## 7. CONSENT (ICF) PROCESS

- Informed consent will be obtained by the research coordinator or PI and documented via a signed consent form, and stored in a locked room.
- The consent will be obtained in-person when the patient arrives for their routine lab tests at SMH or routine clinic visit at the SMH Kidney Clinic (AC3) or Highland Hospital.
- To minimize coercion, the research coordinator, the PI or co-investigator who is not the patient's nephrologist, will explain to the patient the purpose of the study and go over the consent form, and give them the opportunity to ask questions. The patient will also be given the opportunity to take the consent form home with them and take as much time needed to look

- over the consent form.
- If more time is requested by the patient, further follow-ups will occur over the phone or zoom to answer questions, concerns, and discuss participation.
- The research coordinator will ask the patient to summarize the study to ensure their understanding.
- The Investigator or research coordinator will give a copy of the signed consent form to the subject and store the original appropriately in a cabinet in a locked room. If the subject has given permission to use email, the signed consent form will be scanned and emailed to them.
- A check-box for consent to contact subjects for future research will be an option with consent for this study.

**Certificate of Confidentiality:**

The study is funded by the National Institute of Health, and therefore the Certificate of Confidentiality (CoC) is automatically included as part of the notice of award. Language regarding the Certificate of Confidentiality will be included in the consent form.

## **8. STUDY PROCEDURES**

A total of 4 in-person visits and 3 phone call visits will occur for the Phase II study. The baseline (month 0), first-, third-, and sixth-month visits are expected to last about 1 hour and will occur at the labs at SMH, and AC3 clinic in SMH, or Kidney clinic in Highland Hospital. The second-, fourth-, and fifth-month visits are anticipated to last about 30 minutes on the phone.

A 6-month **randomized, double-blind, placebo-controlled study** with Avmacol ES will be conducted. The study will include:

1. Pre-screening
2. Informed consent and buccal swab to determine GSTM1 genotype
3. Randomization: Patients will take the medication or placebo for 6 months, and continue to receive standard of care for CKD
4. Clinic visits for blood pressure (BP) check, labs (urine, blood) at baseline (month 0), months 1, 3, and 6. Kansas City Cardiomyopathy and NIH PROMIS questionnaires administered in-person via paper or REDCap. Side effects and adverse events (AEs) assessment; gastrointestinal (GI), heart failure symptoms
5. Phone call visits and paper/REDCap questionnaires at months 2, 4, 5: Kansas City Cardiomyopathy and NIH PROMIS questionnaires will be offered via REDCap surveys or paper copies depending on participant preference. Side effects and adverse events (AEs) assessment; gastrointestinal (GI), heart failure symptoms will be monitored

Subjects will be provided a yearly calendar to mark the days they consume the tablets and will be asked to have it available with them at each visit to monitor tablet compliance. They will also be provided a reusable medication tracker called Take-n-slide. This product is provided free of cost by the company in exchange for a simple, 5-question survey from the study subjects. The survey will be conducted approx. 1 month after the study subjects start taking the tablets, and they can keep the tracker afterwards for their use.

**1. Pre-Screening:** Demographics and medical history will be obtained using eRecord EMR. Each week, using the inclusion and exclusion criteria, the research coordinator will screen for patients who have a scheduled appointment in our Kidney Clinic within the next 4 weeks.

- The eGFR result should be within a 60-day window at the time of screening. If eGFR testing was performed longer than 60 days, the research coordinator will reach out to the patient's provider to ask when another eGFR will be obtained as part of the patient's standard of care and will follow

up.

- Our research coordinator will use eRecord EMR to screen patients for enrollment based on inclusion and exclusion criteria listed above in section #5. Each week, the research coordinator (RC) will screen subjects scheduled to visit to Kidney Clinic within the upcoming 4 weeks for enrollment. The RC will discuss with [name], who will make the final decision for inclusion and exclusion.
- The pre-screening data for potential subjects who choose not to participate or are ineligible will be deleted.

3. Informed consent and buccal swab for *GSTM1* genotyping: Buccal (cheek) swab sample will be obtained from subject: To extract DNA for *GSTM1* genotyping to assess the effect of *GSTM1* genotype on clinical and biochemical response. Genotyping will be performed as previously done. Each study participant will be assigned a subject ID by the RC after obtaining informed consent. The testing supplies for the buccal swab will be labeled by subject ID only and the lab will perform the genotyping.

3. Randomization: Randomization will be performed by the Investigational Drug Service (IDS) who will be provided the patients' CKD stage. The investigators and subjects will be blinded to the randomization of the study supplement and placebo.

At the onset, the IDS will be provided the CKD stage of each study participant (Stage 3 eGFR 30 - < 60 ml/min/1.73 m^2, Stage 4  $\geq$  20 – 29 ml/min/1.73 m^2), The URM Clinical Research Pharmacy and IDS will assist us in the randomization and dispensing process (their efforts are included in the NIH budget). The research team, healthcare providers and participants will be blinded to treatment assignment. Based on our patient mix in our clinic, we expect ~ 60% will be Caucasian, 40% will be AA, and ~ 50% will be female in each group.

While randomization will not be determined by *GSTM1* genotype, we will explore the effect of the genotype on response to treatment. After consent, *GSTM1* genotype will be determined from DNA extracted from buccal swab at a routine clinic visit. *GSTM1* genotype is for research purpose only and will be performed in [name] laboratory using established protocol 

*The Biomarker lab tests* refer to markers of oxidative stress (plasma hydrogen sulfide (H2S), plasma and urine 8-isoprostane, podocyturia (urine nephrin) to assess glomerular damage, and inflammation (plasma interleukin-6 (IL-6)) will be assessed. Peripheral blood mononuclear cells will be extracted from whole blood and saved for analysis of mRNA levels of cytoprotective enzymes (NQO1, HO-1, AKR1C1, GSTM1), and heat shock proteins (HSP27 and HSP70) . The plasma H2S testing will be performed on coded samples at Cedar-Sinai and there is an MTA for it.

We will perform a urine pregnancy POCT for subjects of child-bearing potential, unless subject reports having had a hysterectomy or if subject is over 50 years of age and the last menstrual cycle was two or more years ago.

Note:

1. If patient gets their labs done before their routine clinic visit, consent will be obtained at the time they come in for their labs (if SMH). If they get their routine SOC labs done at a location that is not SMH i.e. [name] before their routine clinic visit, they will be asked to provide another blood and urine sample (for biomarker lab tests only) at SMH and the research study will pay for them.
2. Patients from non-SMH locations will be asked to travel to SMH as blood samples need to be processed at [name] research lab immediately after blood draw.
3. If the subject decides to have their routine clinic visits and/or SOC lab tests done at a non-SMH location, the study coordinators will collect this data from provider ordered SOC tests from EMR.

For each lab visit related to the study, the study coordinators will carry the requisition that lists the tests to be performed by the URM Central Lab and who would be billed (patient's insurance or research study). For example, if the patient has already had their SOC tests done, the study coordinators will indicate on the requisition that they need labs (blood and urine) for the biomarker lab tests only and it is to be billed to the research study.

On UR Box, the study coordinators will keep track of whether each lab visit was paid for by the patient's health insurance or the research study.

*Questionnaires at baseline visit & each month after:*

In addition, the Global Health, NIH PROMIS, and modified Kansas City Cardiomyopathy questionnaires, will be offered either via paper and phone or as a REDCap survey. Side effects and adverse events (AEs); gastrointestinal (GI), heart failure symptoms will be assessed.

Subjects will be asked to bring the supplement package so the study team can account for the number of tablets taken at the 1st, 3rd, and 6th month visits.

- II. Phone calls at months 2, 4, and 5:** Phone call to assess for any AEs and GI and heart failure symptoms using questionnaires. Study participants will be given the option of answering the questionnaires on the phone or via a REDCap survey.

**Health Questionnaires:** Each subject will be asked to complete three health related surveys to monitor clinical status and symptoms. These are offered electronically in REDCap using an electronic device, or in paper copies and verbally answered over the phone. Copies will also be offered through mail or email. Subjects are expected to complete the general questionnaire once a month. Each form is expected to take 20 minutes to complete.

1. **General Questionnaire:** Brief questionnaire of how the subject feels, including any new symptoms and intake of cruciferous vegetables over the last month.
2. **NIH PROMIS Questionnaire:** Questionnaire for gastrointestinal symptoms.
3. **Kansas City Cardiomyopathy Questionnaire (Modified):** Questionnaire for heart failure symptoms.

**Blood Samples:** Blood collection will involve one venipuncture 20 mL blood sample obtained at baseline visit, and 1st, 3rd, and 6th month. The samples may be obtained at the Clinical Research Center, or Strong Memorial Hospital Outpatient Lab.

**Urine Samples:** Urine collection will involve one sample of a minimum 10 mL obtained at baseline visit, and 1st, 3rd, and 6th month. Samples from subjects of child-bearing potential will also be obtained for pregnancy POCT, performed by RC or Lab staff. The samples may be obtained and processed at the Clinical Research Center, or Strong Memorial Hospital Outpatient Lab or AC1.

Whole blood will be processed for plasma and serum, divided in 200 ul aliquots, and urine will be divided in 2 mL aliquots, frozen, and stored at -80°C for later processing and analysis in [name] lab at the University of Rochester Medical Center.

**Medical Record EMR:** No research data (*GSTM1* genotype or biomarker levels) will be included in the subject's medical record. Laboratory data that are part of the patients' clinical care will be conveyed to the patients and providers as standard of care in their EMR. For the study, we will collect demographic information, including age, sex, height, weight, race, past medical history – specifically history of hypertension, heart failure, and etiology of kidney disease, if any - and blood pressure data. While not anticipated, incidental findings that might have health consequences for the individual subject will be addressed as clinically indicated.

As this is conducted under an IND, the samples will be stored for 2 years after marketing approval or for 5 years, whichever is later. Should additional tests be deemed informative or mechanistic to enhance further understanding, we will contact the subjects while samples are still available. Samples will be destroyed after 5 years.

**Genetic Research Procedures:** As mentioned above, the *GSTM1* null genotype is quite common in human populations, with 50% Caucasians and 27% African Americans being homozygous for the *GSTM1* (0/0) allele. Whole genomic sequencing will not occur. No genetic counseling will be provided to the subject. We will genotype *GSTM1* to assess whether it influences any biomarker-related response to Avmacol ES.

## Schedule of Assessments

Visit Month	Window	Location	Action items for RC	Tests & Samples
Baseline/ Month 0	N/A	SMH AC3/Highland Hospital	
 
• Informed consent
 
• Buccal swab, note eGFR (CKD stage)
 
• Dispense 3-month supply of supplement
 
• Reusable medication tracker Take-n-slide and calendar
 
	
 
• BP in AC3
 
• Blood, Urine, (Pregnancy Test)
 

Visit Month	Window	Location	Action items for RC	Tests & Samples
Month 0.5	+2 weeks	Phone call	
 
• Side effects and adverse events (AEs) assessment
 
	None
Month 1	+/- 2 weeks	AC3 Strong + Laboratory (Separate room)	
 
• Side effects and adverse events (AEs) assessment
 
• GI & heart failure symptoms questionnaires
 
• Review of tablet intake
 
• Pregnancy test
 
• Take-n-slide survey
 
	
 
• BP in AC3
 
• Blood, Urine, (Pregnancy Test)
 

Month 2	+/- 2 weeks	Phone call	
 
• Side effects and adverse events (AEs) assessment
 
• GI & heart failure symptoms questionnaires
 
• Review of tablet intake
 
	None
Month 3	+/- 2 weeks	AC3 Strong + Laboratory	
 
• Side effects and adverse events (AEs) assessment
 
• GI & heart failure symptoms questionnaires
 
• Review of tablet intake
 
• Pregnancy test
 
• Refill 3-month supply of supplement
 
	
 
• BP in AC3
 
• Blood, Urine, (Pregnancy Test)
 

Month 4	+/- 2 weeks	Phone call	
 
• Side effects and adverse events (AEs) assessment
 
• GI & heart failure symptoms questionnaires
 
• Review of tablet intake
 
	None
Month 5	+/- 2 weeks	Phone Call	
 
• Side effects and adverse events (AEs) assessment
 
• GI & heart failure symptoms questionnaires
 
• Review of tablet intake
 
	None

Month 6	+/- 2 weeks	AC3 Strong + Laboratory	
 
• Side effects and adverse events (AEs) assessment
 
• GI & heart failure symptoms questionnaires
 
• Review of tablet intake
 
• Pregnancy test
 
	
 
• BP in AC3
 
• Blood, Urine, (Pregnancy Test)
 

---------	-------------	-------------------------	---	---

## 9. RISKS TO SUBJECTS

### Sulforaphane/Avmacol ES (Study Drug)

There are some potential risks to participants since we are introducing a well-tolerated study drug in other clinical trials but has not been previously tested in CKD patients. We take careful precautions by first establishing an optimal dose of Avmacol ES in CKD patients using reported peak plasma concentrations in trials that were conducted in patients without kidney disease. Based on the multiple clinical trials that have been done with Avmacol or the actual sulforaphane compound in other diseases, we do not anticipate any serious risks. The most common side effects are gastrointestinal, including nausea and dyspepsia, which are ameliorated when taken after a meal.

Although not reported in any earlier trial nor in our PK phase of the study, there is the possibility of an allergic reaction to the study drug. This reaction may be mild, such as a skin rash, or more severe symptoms like swelling of the throat, low blood pressure, and shortness of breath. In rare cases, a severe reaction could cause death.

### Risks of Blood Draw

The most common risk is pain, bleeding, or bruising at the site of the blood draw. Other risks include redness, and swelling of the vein and infection, and a rare risk of fainting.

### Risks of Buccal Swab

The risk is minimal. There is risk of not obtaining adequate sample for DNA extraction.

### Risks of Urine Sample

The risk is minimal. There is risk of spilling urine onto clothes.

**Risks of Pregnancy:** The effect of sulforaphane on the fetus is not known. The patient will be advised to immediately stop taking the supplements if pregnancy is suspected and notify the research team.

### Risk of Disclosure of Privacy and Confidentiality

Other potential risks involve violations of confidentiality. Procedures for assuring confidentiality are discussed below.

### Risks to Social/Emotional Well-Being

We do not anticipate any psychological, social or legal risks beyond those related to participation in a clinical study.

### Risks of Questionnaires

There are no anticipated risks for subjects to complete the requested questionnaires.

Patients will be informed that declining to participate in this study will not impact their care whatsoever.

## 10. POTENTIAL BENEFITS TO SUBJECTS

Subjects may or may not benefit from being in this research study. This study is conducted to determine safety and efficacy of the supplement on markers of inflammation and oxidative stress. The potential benefit to you might be improved levels of markers of oxidative stress and inflammation, and decreased kidney disease progression rate. Positive results from this study would provide a rationale for a much larger and longer study to determine if the medication can slow down kidney disease progression.

## 11. COSTS FOR PARTICIPATION

There is no cost for participation of the study. Avmacol ES will be provided by Nutramax without cost to the patients.

- *The Standard of Care (SOC) lab tests:* The subject and/or their insurance company will be responsible for the costs of these tests.
- *The Clinical Research lab tests:* The research study will pay for all bills associated with these tests.
- *The Biomarker lab tests:* The research study will pay for any bills associated with these tests.

## 12. PAYMENT FOR PARTICIPATION

For this study, we will use a subject payment system called Advarra Participant Payments. The system allows three ways to provide payment. The subjects can choose: a reloadable debit card; direct deposit; or mailed paper checks.

Payment: Compensation will be divided into four payments of \$25.00 at month 0 (baseline), month 1, month 3, and month 6. Subjects who are withdrawn or voluntarily withdraw from the study due to side effects will also receive the full compensation of \$100.

Parking pass: Study participants will be provided a parking pass for their study visits to the SMH. Patients from non-SMH locations who travel to SMH for their labs (blood, urine) and BP checks will also be provided a parking pass. For participants with severe ambulatory challenges, an option to be reimbursed for valet parking service will be offered.

Bus pass: An option for a bus pass will be provided to study participants

## 13. SUBJECT WITHDRAWALS

1. Participants' decision to withdraw from the study for any reason
2. Development of side effects that are not resolved by dose reduction
3. Failure to adhere to the study protocol
4. Relocation resulting in inability to follow up per protocol
5. Become pregnant
6. New diagnosis of heart failure, cardiovascular event, life threatening infection, or cancer

In the event that a subject drops out the study due to reasons listed above, we will recruit an additional patient to replace.

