#### 4.1 SUBJECT POPULATION

We will enroll 88 adult patients followed in the Kidney Clinic in AC-3, Highland Hospital, Brockport, St. James, and FF Thompson with chronic kidney disease. Evaluable subjects who withdraw from the study will be replaced by subjects with CKD stage 3 or 4 to meet the enrollment goal. We will recruit patients of any gender, race, and socioeconomic status.

Enrollment will conclude by November 15, 2024 to complete subjects' 6-month timeline by April 30, 2025. At that point the PI is transferring out of URM.

**Vulnerable Subjects:** We do not plan to include vulnerable subjects such as children, pregnant women, fetuses, decisional impaired adults, or prisoners. Employees (physicians/fellows) will be assured that taking part in research is not a part of their duties, and refusing to participate in the study will not affect their job. To ensure their autonomy, the research coordinators or the PI who is not the patient's nephrologist will consent them.

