#### 4.2 STUDY INTERVENTIONS

Study Drug: Avmacol Extra Strength (ES) tablets

IND # 158689

IND Holder: [name]

The study will be registered on ClinicalTrials.gov. For this double-blind and randomized, placebo-controlled trial, approximately half of the subjects will be randomized to either 4 tablets of Avmacol ES, or 4 tablets of placebo daily for 6 months. To adjust to the supplements, subjects will start the study at a dose of 2 tablets once daily for a week and then 4 tablets once daily after that for a total study period of 6 months. Nutramax will provide the tablets of both active supplement and matched placebo in bottles shipped directly to URM Clinical Research Pharmacy Investigational Drug Services (IDS) to store, monitor, and dispense.

If the subjects experience side effects at a dose of 4 tablets together daily, they will be asked to stop taking the supplements for a week and resume at a dose of 3 tablets together daily. If they experience side effects at this dose, this will be asked to stop taking the supplements for a week again and resume at a dose of 2 tablets together daily. If they still experience side effects, they will be withdrawn from the study for safety. In case of a health emergency, the subject's healthcare provider and/or nephrologist will be unblinded to the study treatment (supplement versus placebo) by paging the IDS office.

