If a CKD stage 4 patient drops out, a CKD stage 3 patient may be enrolled to make up for the drop-out to reach the total of 88 study participants. Treatment assignments will be performed by the IDS, and the study team will remain blinded.

With 44 patients in Avmacol ES group and 44 in placebo group who would complete the study, we expect to have power to detect the difference in 8-isoprostane between the two groups. The power analysis was performed using two-sample *t*-test with 5% type I error. The effect size is considered close to medium effect, which is appropriate for this pilot study as we intend to establish preliminary evidence of treatment effect of Avmacol ES. As mentioned above, *the Kidney Clinic in AC3 sees ~ 800-900 patients with CKD a month and ~ 60% of patients are in the CKD Stages 3-4 stages. Thus, in addition to Highland Hospital, we should be able to easily achieve our recruitment target.*

In the event that patients drop out the study due to relocation or loss to follow up, we will recruit additional patients. Based on the number of dropouts at 12 months into the study, we will recruit an extra number of patients commensurate with the dropout rate such that we will have the anticipated number of patients (44 in each group) who will complete the study in 24 months.

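### Subjects withdrawn for side effects, non-adherence or clinical events leave the study and are replaced towards 44 completers per arm, with no follow-up after withdrawal, analysis set or safety population stated

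*Combined protocol and SAP*

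**What the plan says.** Section 4.2 sets out stepwise dose reduction and then: "If they still experience side effects, they will be withdrawn from the study for safety". The withdrawal is from the study, not only from tablets.

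Section 13 lists further grounds, among them "Development of side effects that are not resolved by dose reduction", "Failure to adhere to the study protocol" and "New diagnosis of heart failure, cardiovascular event, life threatening infection, or cancer". It then applies one rule to the whole list: "In the event that a subject drops out the study due to reasons listed above, we will recruit an additional patient to replace".

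Three places state who is replaced, and they differ:
- Section 4.1: "Evaluable subjects who withdraw from the study will be replaced by subjects with CKD stage 3 or 4 to meet the enrollment goal". The qualifying word at the start is not defined.
- Section 13: every listed reason.
- Section 18, power calculation: one paragraph replaces any dropout (its example is 8 of 88, giving 96 enrolled). A later paragraph names only relocation or loss to follow-up, with extra recruitment "such that we will have the anticipated number of patients (44 in each group) who will complete the study in 24 months".

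The schedule of assessments in Section 8 has no visit or call for a subject who has been withdrawn. The statistical analysis text in Section 18 plans t-tests or regression on plasma 8-isoprostane at each time point, a linear mixed model over all visits, and a descriptive and chi-square comparison of adverse events. It names no analysis population and no handling of missing values.

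**The concern.** Most of the listed reasons arise after randomisation and may be linked to treatment. Section 9 names gastrointestinal effects as the commonest side effects of the supplement. Heart-failure symptoms are asked about at every scheduled contact from month 1. If subjects leave at different rates or for different reasons in the two arms, those still present at month 6 are no longer the groups that randomisation formed. A new recruit brings the count back to 44 but does not supply the missing outcome of the person who left.

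Safety and tolerability is Aim 1, and the subjects who tolerate the tablets least are the ones whose later course is not scheduled to be observed. Because no safety population is named, it is also unclear whether adverse-event rates are taken over the 88 who complete or everyone enrolled.

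Section 14 allows the investigators to be unblinded before analysis. An analysis population not fixed in advance could therefore be settled with the assignments known.

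**Working it through.** **1. The plan's own figure.** Section 18 assumes 400 v 300 pg/mL, SD 150, and a two-sample t-test at 5% (two-sided assumed). The standardised effect is 100/150 = 0.667. With 44 per arm, the noncentral t gives 87.1% power. No target power is stated, so 88 can be neither confirmed nor refuted; it corresponds to about 87% if all 88 complete.

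**2. What becomes of a leaver's data under the text as written.**
- The event that triggers withdrawal: recorded (Section 4, Aim 1, documents any side effect).
- Visits before withdrawal: available to the mixed model.
- Visits and harms after withdrawal: no collection is described.
- Month-6 t-test or regression: all leavers are absent.
- A subject who leaves before month 1 has no post-baseline 8-isoprostane value.

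**3. Adverse-event denominator.** In the plan's example of 8 dropouts, 88 complete and 96 are enrolled. The same event count over 88 gives a rate 96/88 = 1.09 times that over 96. The plan does not say which applies.

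**4. Possible bias in a completers-only comparison with no true effect.** The documents give neither dropout by arm nor any link between leaving and 8-isoprostane, so these are assumptions: 8 leavers in total (the plan's example), 44 per arm as the base, and a correlation ρ of 0.3 to 0.5 between the tendency to leave and 8-isoprostane, the same in both arms. With q = leavers/44 and z the normal quantile of 1 − q, completers in an arm are shifted by ρ·φ(z)/(1 − q) SD. The bias is the difference between arms times 150 pg/mL.

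Values of φ(z)/(1 − q): 2 leavers 0.1001; 3 leavers 0.1412; 4 leavers 0.1800; 5 leavers 0.2171; 6 leavers 0.2531; 8 leavers 0.3227.

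Example, 6 v 2: 0.2531 − 0.1001 = 0.1530. At ρ = 0.3 this is 0.0459 SD, or 6.89 pg/mL; at ρ = 0.5 it is 0.0765 SD, or 11.48 pg/mL.

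| Split of 8 leavers | Bias, pg/mL (ρ 0.3 to 0.5) | False-positive rate, 44 per arm |
|---|---|---|
| 4 v 4 | 0 | 5.0% |
| 5 v 3 | 3.42 to 5.70 | 5.1% to 5.4% |
| 6 v 2 | 6.89 to 11.48 | 5.5% to 6.5% |
| 8 v 0 | 14.52 to 24.21 | 7.3% to 11.6% |

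The last column is the rejection rate of the two-sided 5% t-test when the true shift equals the bias.

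**5. Power if everyone randomised is kept.** Assume leavers show no effect and 44 completers per arm are still sought.
- 8 of 96 leaving: 48 per arm, difference 100 × (1 − 8/96) = 91.7 pg/mL, power 84.2%.
- 20% leaving: 44/0.8 = 55 per arm, difference 80 pg/mL, power 79.2%.

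**6. Cost of not balancing completers.** At the assumed effect, 40 v 48 gives 86.8% power against 87.1% for 44 v 44.

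**The case against.** The best defence is that the plan does not restrict its analysis to completers. The 44 per group is a recruitment target. The mixed model can use the earlier visits of those who leave. Adverse events are to be documented and compared by group with no exclusion of withdrawn subjects, and the DSMB sees unblinded adverse-event data. Section 18 also calls this a pilot, and enrolment closes on November 15, 2024, so later dropouts cannot be replaced.

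Much of this stands, and it rules out several stronger readings that a reader might infer:
- *That the primary comparison is one of completers only.* No section says so. The fault is that the population is undefined.
- *That harms are dropped from Aim 1.* The triggering event has been observed and nothing removes it. What can be lost is harm arising later.
- *That replacements are steered to the depleted arm and so are not randomised.* Reaching 44 completers in each arm under unequal dropout invites this, but Section 18 says only that the pharmacy service makes the assignments with the team blinded. Enrolling until both arms reach 44 would also meet the target.
- *That one arm drifts to milder disease.* Section 18 does allow it: "If a CKD stage 4 patient drops out, a CKD stage 3 patient may be enrolled to make up for the drop-out". Drift in one arm alone would also need unequal stage 4 dropout and steering. Adjustment for baseline imbalance is a partial safeguard.
- *That the bias favours Avmacol.* Nothing links gastrointestinal intolerance to 8-isoprostane, and cardiovascular events could be commoner on placebo.

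What the defence does not answer is that withdrawal from the study is a written rule. The mixed model cannot supply values after withdrawal, and the month-6 tests contain no leavers.

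**Conclusion.** The concern holds in this form. Subjects are withdrawn from the study for reasons that may depend on treatment and are replaced towards a completer target. Follow-up after withdrawal, the efficacy set, the safety population and the missing-data method are all unstated. The three replacement rules (Sections 4.1, 13 and 18) conflict and must be reconciled.

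The size is uncertain and may be nil. It is zero if leaving is equal and equally selective in both arms, small at moderate imbalance, and reaches about a quarter of the assumed 100 pg/mL effect only if all 8 leavers come from one arm and ρ is 0.5. These figures rest on an assumed correlation and on an analysis of completers, which the plan neither states nor excludes. The reason to act is that the gap touches Aim 1 and the month-6 comparison directly and is cheap to close.

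**What to change.** 1. Separate stopping tablets from leaving the study in Sections 4.2 and 13. Those who stop tablets are asked to keep the scheduled month 1, 3 and 6 samples and the adverse-event contacts unless they withdraw consent. The rules on who stops tablets stay as they are.
2. In Section 18, state that all randomised subjects are analysed in their assigned arm, using all available visits in the mixed model. State that everyone who took study tablets, including those later replaced, counts in the safety denominators. Fix this before unblinding.
3. State that any additional subject takes the next assignment on the same randomisation list, with no balancing of completers by arm. Give one replacement rule across Sections 4.1, 13 and 18, and define or remove the term evaluable.

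Cost: wording in four sections, and some off-treatment visits at time points already in the schedule. Section 12 already pays full compensation to those withdrawn for side effects. The downside is that the estimate will include off-treatment data and may be smaller, with the loss of power shown in step 5 of the working.
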